14.3 Safety Monitoring

Adverse events will be monitored on an ongoing basis by the central office and their frequencies reported annually at investigators' meetings. Adverse events will be categorized using the NCI Common Terminology Criteria for Adverse Events (CTCAE). The worst event for each patient in each category or subcategory will be described. Both events related and unrelated to treatment will be captured.

Clinical and laboratory data will be tabulated and compared to normal ranges for the institution.

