1.2 Secondary Objectives

- To assess whether tumour texture parameters from a CT scan can correlate with time to disease progression in patients with metastatic melanoma being treated with pembrolizumab.
- To assess duration of response (DoR).
- To assess overall response rate (ORR, PR, CR).
- To assess overall survival (OS).
- To compare cost per quality adjusted life years (QALY) between pembrolizumab and dacarbazine.
- To compare cost per quality adjusted life years (QALY) between pembrolizumab and ipilimumab.
- Toxicity using the CTCAE v.4.

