5.1.6 Laboratory Requirements (must be done within 7 days prior to registration)

Hematology:	Absolute neutrophils (ANC)	$\geq 1.5 \times 10^9/L$
	Platelets	$\geq 100 \times 10^9/L$
	Hemoglobin	$\geq 90 \text{ g/L}$ or $\geq 5.6 \text{ mmol/L}$ (without transfusion or EPO dependency)
Chemistry:	Serum creatinine	$\leq 1.5 \times \text{ULN}$
	OR	OR
	Measured or calculated creatinine clearance	$\geq 60 \text{ mL/min}$ for subject with creatinine levels $> 1.5 \times \text{ULN}$
	Serum Total Bilirubin	$\leq 1.5 \times \text{ULN}$
	OR	OR
	Direct bilirubin	$\leq \text{ULN}$ for subjects with total bilirubin levels $> 1.5 \times \text{ULN}$
	AST and ALT	$\leq 2.5 \times \text{ULN}$ ($\leq 5 \times \text{ULN}$ for subjects with liver mets)
	Albumin	$\geq 25 \text{ g/L}$

5.1.7 Women/men of childbearing potential must have agreed to use a highly effective contraceptive method. A woman is considered to be of "childbearing potential" if she has had menses at any time in the preceding 12 consecutive months. In addition to routine contraceptive methods, "effective contraception" also includes heterosexual celibacy and surgery intended to prevent pregnancy (or with a side-effect of pregnancy prevention) defined as a hysterectomy, bilateral oophorectomy or bilateral tubal ligation, or vasectomy/vasectomized partner. However, if at any point a previously celibate patient chooses to become heterosexually active during the time period for use of contraceptive measures outlined in the protocol, he/she is responsible for beginning contraceptive measures.

5.1.8 Women of childbearing potential will have a serum or urine pregnancy test within 7 days prior to registration to determine eligibility. If the urine test is positive or cannot be confirmed as negative, a serum pregnancy test will be required. This may also include an ultrasound to rule-out pregnancy if a false-positive is suspected. For example, when beta-human chorionic gonadotropin is high and partner is vasectomized, it may be associated with tumour production of hCG, as seen with some cancers. Patient will be considered eligible if an ultrasound is negative for pregnancy.

AMEND #2: 2017-JUL-10

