6.0 PRE-TREATMENT EVALUATION
(See Appendix I)

Investigations		Timing
History and Physical Exam including:	
 history height/weight vital signs (blood pressure and pulse) ECOG performance status documentation of all measurable and non-measurable disease clinical tumour measurements (if applicable) 	Within 14 days prior to registration
Hematology	
 CBC, differential, platelets 	Within 7 days prior to registration
Biochemistry	
 serum creatinine (or measured or calculated creatinine clearance) electrolytes (sodium, potassium, chloride, bicarbonate) bilirubin alkaline phosphatase AST, ALT LDH phosphorous calcium magnesium albumin TSH, FT3, FT4 HCV, HBV screening serology (if unknown) 	Within 7 days prior to registration
Radiology ¹	
 CT scan with contrast of chest, abdomen/pelvis other sites as clinically indicated 	Within 28 days ² prior to registration
Other Investigations	
 pregnancy test* (if applicable) ECG (if not done within 6 months) 	Within 7 days prior to registration
Economics	
 Health Utilities Index (EQ-5D) 	
Adverse Event ³	
 baseline adverse event evaluation (to document residual adverse event from previous therapy and baseline symptoms) 	

1 To ensure comparability, baseline and subsequent CT scans to assess response must be performed using identical techniques (i.e. scans performed immediately following bolus contrast administration using a standard volume of contrast, the identical contrast agent, and preferably the same scanner – see Appendix VII).
 2 Thirty-five days if negative
 3 Adverse events will be recorded and graded according to the NCI Common Terminology Criteria for Adverse Events (CTCAE) (Appendix V).
 * These tests are considered study-specific and must be performed AFTER the informed consent form has been signed.

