Pneumonitis	2	Toxicity resolves to Grade 0-1. For grade 2 events treat with systemic corticosteroids. When symptoms improve to grade 1 or less, steroid taper should be started and continued over no less than 4 weeks.	Toxicity does not resolve within 12 weeks of last dose or inability to reduce corticosteroid to 10 mg or less of prednisone or equivalent per day within 12 weeks
	3-4	Permanently discontinue	Permanently discontinue
Renal Failure or Nephritis	2	Toxicity resolves to Grade 0-1	Toxicity does not resolve within 12 weeks of last dose or inability to reduce corticosteroid to 10 mg or less of prednisone or equivalent per day within 12 weeks
	3-4	Permanently discontinue	Permanently discontinue
All Other Drug-Related Toxicity	3 or Severe	Toxicity resolves to Grade 0-1	Toxicity does not resolve within 12 weeks of last dose or inability to reduce corticosteroid to 10 mg or less of prednisone or equivalent per day within 12 weeks
	4	Permanently discontinue	Permanently discontinue

Note: Permanently discontinue for any severe or Grade 3 drug-related AE that recurs or any life-threatening event.

^a For patients with liver metastasis who begin treatment with Grade 2 AST or ALT, if AST or ALT increases by greater than or equal to 50% relative to baseline and lasts for at least 1 week then patients should be discontinued.

^b If symptoms resolve within one hour of stopping drug infusion, the infusion may be restarted at 50% of the original infusion rate (e.g., from 100 mL/hr to 50 mL/hr). Otherwise dosing will be held until symptoms resolve and the subject should be premedicated for the next scheduled dose; Refer to Section 8.3.1, Infusion Related Reactions Table for further management details.

^c Patients with intolerable or persistent Grade 2 drug-related AE may hold study medication at physician discretion. Permanently discontinue study drug for persistent Grade 2 adverse reactions for which treatment with study drug has been held, that do not recover to Grade 0-1 within 12 weeks of the last dose.

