10.0 CRITERIA FOR MEASUREMENT OF STUDY ENDPOINTS

10.1 Definitions

10.1.1 Evaluable for adverse events. All patients will be evaluable for adverse event evaluation from the time of their first treatment.

10.1.2 Evaluable for response. All patients who have received at least one cycle of therapy and have their disease re-evaluated will be considered evaluable for response (exceptions will be those who exhibit objective disease progression prior to the end of cycle 1 who will also be considered evaluable). Patients on therapy for at least this period and who meet the other listed criteria will have their response classified according to the definitions set out below [Seymour 2016].

Response and progression will be evaluated in this study using the revised international criteria (1.1) proposed by the RECIST (Response Evaluation Criteria in Solid Tumours) committee as well as the modified iRECIST guidelines [Seymour 2016]. Investigators should note the different requirements for confirmatory scans as well as follow up for the two criteria.

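### The toxicity summary in 14.3 does not use the baseline grade the trial collects, so abnormalities that persist from entry would be included as on-study toxicity (minor)

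*Combined protocol and SAP*

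**What the plan says.** Toxicity is the last of the secondary objectives in 1.2: "Toxicity using the CTCAE v.4". The only text on how it is to be analysed is 14.3 Safety Monitoring, which has three relevant statements:

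- On adverse events: "The worst event for each patient in each category or subcategory will be described".
- On attribution: "Both events related and unrelated to treatment will be captured".
- On laboratory data, as a separate sentence: "Clinical and laboratory data will be tabulated and compared to normal ranges for the institution".

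Baseline grade, change from baseline, treatment-emergent events and shift tables are not mentioned there, and no other section brings them into the analysis.

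Baseline information is collected. Section 6.0 requires a "baseline adverse event evaluation (to document residual adverse event from previous therapy and baseline symptoms)", graded by CTCAE, with haematology and biochemistry within 7 days before registration. Section 5.1.6 admits abnormal values at entry: hemoglobin from 90 g/L, platelets from 100 x 10^9/L, creatinine and bilirubin up to 1.5 x ULN (with alternative criteria above that), albumin from 25 g/L, and AST/ALT up to 2.5 x ULN, or 5 x ULN "for subjects with liver mets". Footnote a to the table in 8.3 has a provision that begins "For patients with liver metastasis who begin treatment with Grade 2 AST or ALT". Section 10.1.1 sets the start of the evaluation period: "All patients will be evaluable for adverse event evaluation from the time of their first treatment".

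**The concern.** A worst-grade summary describes what was seen on study. It describes toxicity only if what the patient brought into the study is set aside. Here the protocol expects some patients to arrive with graded abnormalities and records them, but does not tell the analyst to use that record. A patient whose AST is Grade 2 at entry and stays at Grade 2 would have a worst on-study grade of 2 if it is reported as an adverse event. A stable hemoglobin of 105 g/L would be flagged wherever the institution's lower limit lies above that value.

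Pembrolizumab is the only treatment in the trial, so no concurrent arm shows how much of each frequency is background. Reported frequencies could therefore overstate toxicity in the categories where entry abnormalities are likely: hepatic, haematologic and symptom categories.

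**Working it through.** The plan gives no figure on this point, so there is none to reproduce. The check has two parts.

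**1. The text**

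| Step | What the documents provide | Baseline used? |
|---|---|---|
| Entry (5.1.6; 8.3 footnote a) | Abnormal laboratory values allowed; Grade 2 AST/ALT at start foreseen | Not applicable |
| Collection (6.0, Appendix I) | CTCAE-graded baseline events; baseline laboratory values | Recorded |
| Treatment decision (8.3 footnote a) | A rise judged relative to baseline | Yes |
| Evaluation period (10.1.1) | From first treatment | No |
| Adverse event summary (14.3) | Worst event per patient per category, related and unrelated | No |
| Laboratory summary (14.3) | Comparison with institutional normal range | No |

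The period in 10.1.1 removes events that ended before the first dose. It does not remove an abnormality still present after it. The baseline-relative rule in footnote a governs discontinuation, not analysis.

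**2. The size**

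For one category, let b be the prevalence at entry and t the proportion of patients without the abnormality who develop it on treatment. Among those with it at entry, let r be the share in whom it is gone once treatment starts, and w the share in whom it worsens.

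- Rate under the worst-event rule: b(1 − r) + (1 − b)t
- Rate counting only new or worsened events: bw + (1 − b)t
- Difference: b(1 − r − w)

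If the abnormality persists unchanged (r = w = 0), the difference is exactly b. Resolution or worsening makes it smaller. The documents give none of these quantities, so the values below are assumptions, with r = w = 0 and N = 84 (the recruitment target in 14.2).

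| b | t | Worst-event rule | New onset only | Excess |
|---|---|---|---|---|
| 10% | 10% | 0.10 + 0.90 x 0.10 = 19.0% (about 16) | 9.0% (about 8) | 10 points |
| 20% | 10% | 0.20 + 0.80 x 0.10 = 28.0% (about 24) | 8.0% (about 7) | 20 points |
| 30% | 10% | 0.30 + 0.70 x 0.10 = 37.0% (about 31) | 7.0% (about 6) | 30 points |

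Over b from 10% to 40% and t from 5% to 20%, the worst-event rate runs from 14.5% to 52.0% and the new-onset rate from 3.0% to 18.0%.

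**Hemoglobin illustration.** This is a simulation with no drug effect. It assumes a within-patient SD of 4 g/L, entry at 90 g/L or above, and a lower normal limit of 120 g/L. It counts patients with any on-treatment value below the limit, over 4 to 17 values (52 weeks / 3 is about 17 cycles, a ceiling because many patients stop earlier).

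| Assumed mean (g/L) | Between-patient SD (g/L) | Ever below limit on treatment |
|---|---|---|
| 125 | 15 | 47% to 55% (37% at baseline) |
| 135 | 15 | 24% to 30% (17% at baseline) |
| 145 | 15 | about 9% to 12% |
| 135 | 10 | about 15% to 22% |

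The answer is driven by the assumed mean and SDs, none of which is in the documents. In the first two rows, new low values in patients normal at baseline are 8% to 19% of all patients, or about 10% to 30% of those normal at baseline. Using baseline therefore removes the entry prevalence but leaves the noise from repeated measurement.

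**The case against.** The strongest reply is that 14.3 is silent on baseline and does not direct that baseline findings be counted. That is correct. A reader might infer that the plan defines entry abnormalities as toxicity, but the documents do not say so. What can be said is that they would be included if the rule is applied as written, and that the choice is otherwise left to whoever programs the tables.

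Second, the worst-event sentence governs adverse events only. The laboratory sentence says neither that the worst value is taken nor that an out-of-range value is a toxicity. Flagging a stable low hemoglobin as below range is accurate. This stands: the simulation above illustrates one way of summarising laboratory data and is not the plan's stated rule.

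Third, relatedness is recorded, so a table of related events could leave out stable entry findings. This mitigates in part. However, 14.3 does not restrict the summary to related events, and the laboratory tabulation has no attribution step.

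Fourth, a reader might take the simulated 24% to 55% at means of 125 and 135 g/L as the expected overstatement. It is not: it falls to about 9% to 12% at an assumed mean of 145 g/L. Nor must the no-effect rate always reach the entry prevalence, because residual effects of earlier surgery or palliative radiation, both permitted by 5.1.5, may resolve.

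Lastly, no hypothesis, threshold or stopping rule depends on these frequencies, 14.1 does not list toxicity among its secondary endpoints, and worst grade regardless of attribution is a recognised descriptive summary. This limits the severity but does not remove the point, since the baseline data are already collected.

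**Conclusion.** The point holds as a minor one. As written, 14.3 would include persisting entry abnormalities in the on-study toxicity summary, with no control arm to separate them and no stated use of the baseline grade. For an abnormality that persists unchanged, the overstatement equals its entry prevalence; it is smaller where the abnormality resolves or worsens. That prevalence is not in the documents, so no single figure can be given, and the percentages shown are illustrative only. Attribution may reduce the effect for adverse events. The consequence is confined to a descriptive secondary objective; the primary texture analysis is untouched.

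**What to change.** In 14.3, state that:

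- for each CTCAE category, the worst on-treatment grade counts as an adverse event only if the term is new after first treatment or its grade is higher than the patient's baseline grade;
- laboratory results are shown as shift tables of baseline CTCAE grade by worst on-treatment grade;
- the all-events summary, related and unrelated, is kept as a supplementary table or listing.

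The cost is SAP wording and table programming. Baseline events and laboratory values are already collected, so no new data or visits are needed. The rule removes abnormalities that persist unchanged from baseline. It does not remove all visit-to-visit noise in repeated laboratory values, and the report should say so.

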14.4 Economic Analysis

The purpose of the CCTG economic evaluation in this phase II study is to determine the incremental cost-effectiveness and cost-utility of pembrolizumab from a universal access government payer perspective, over a lifetime time horizon by prospectively collecting resource utilization information during this clinical trial and comparing to data collected from public databases.

In this study, a cost-utility analysis will be conducted to compare the overall cost per quality-adjusted-life-year (QALY) for pembrolizumab individually with dacarbazine and ipilimumab. Case report forms will be used in this study to document non-protocol based health care resource utilization over the course of treatment and follow-up, including outpatient consultations/visits/investigations, inpatient admissions, emergency room visits, supportive care medication for management of toxicity, and investigations/admissions/treatment of adverse events and disease progression. Forms will be ascertained at 12-week intervals while on treatment until disease progression or a maximum period of 12 months. Unit costs for drugs, hospitalizations, and treatments will be ascertained using publically available sources and reported in adjusted Canadian dollars.

Patient preferences while on pembrolizumab, or utilities, will be derived from the EQ-5D questionnaire [*Brooks 1996; Drummond 1997; www.euroqol.org*]. The EQ-5D self-administered questionnaire consists of two pages comprising the EQ-5D descriptive system and the EQ VAS. The EQ-5D descriptive system comprises five dimensions of health (mobility, self-care, usual activities, pain/discomfort, anxiety/depression) and each dimension comprises three levels (no problems, some/moderate problems, extreme problems). The five level score may also be used. A unique EQ-5D health state is defined by combining one level from each of the five dimensions. The EQ VAS records the respondent's self-rated health status on a vertical graduated (0-100) visual analogue scale. The EQ-5D is a validated instrument that has been used in population surveys and clinical trial settings. EQ-5D will be obtained at prescribed intervals. Utilities for patients on dacarbazine and ipilimumab will be obtained from published literature [*Tomme 2014*].

A decision analytic Markov model will be used to extrapolate the costs and survival estimates from the current study (for pembrolizumab) and dacabazine/ipilimumab in order to generate cost/life-year estimates over clinically plausible scenarios. Survival estimates for dacarbazine and ipilimumab will be obtained from previously published randomized controlled trials [*Robert 2011*]. Life-year estimates will be multiplied by time-weighted utility values to generate QALYs. Use of pembrolizumab will be individually compared with dacarbazine and ipilimumab to generate incremental cost effectiveness ratios (ICERs) expressed as cost/QALY.

Deterministic and probabilistic sensitivity analyses using Monte Carlo simulations will be used to explore the robustness of the model to clinically plausible variations in key assumptions and variations in the analytical methods used. Major drivers of medical care costs, including hospitalizations, drug costs, and survival, will be varied +/- 20% and based on reported estimates provided in the literature. Cost effectiveness acceptability curves will be used to understand the impact of different thresholds of cost effectiveness and increase generalizability of results.

